Study Protocol and Statistical Analysis Plan

Official Title:

**An Evaluation of an Integrated Approach to Prevention and Early Intervention
in the Elementary School Years**

ClinicalTrials.gov ID: NCT03132805

PI Name: [name]

Note: There were no amendments for changes in the trial design submitted or approved by the Johns Hopkins Bloomberg School of Public Health Institutional Review Board after the initial release of the ClinicalTrials.Gov protocol on 04/04/2017.

Study Description

Rationale:

There is considerable evidence from long-term longitudinal studies that aggressive/disruptive behavior as early as entrance into elementary school predicts later antisocial behavior, violence, substance abuse and low educational and occupational attainment^{10,11,12,13,14}. In response to that evidence, our Advanced Center for Intervention and Services Research (ACISR), the Johns Hopkins Prevention Intervention Research Center (JHU PIRC), has carried out a series of large scale randomized trials of promising school-based **universal** preventive interventions targeting aggressive/disruptive behavior in elementary school. Each trial has built on the findings of the previous trial in accord with the prevention research cycle as elaborated in the Institute of Medicine Report on *Reducing Risks for Mental Disorders*¹⁵. Although we have found beneficial proximal and distal intervention effects^{10,12,16}, our results point to the need for integrating our universal interventions with evidence-based indicated and early treatment interventions to reduce the number of non-responders and to increase the magnitude of intervention effects. We briefly elaborate below the history of our trials and the findings that formed the basis for this trial.

The 1st Generation JHU PIRC Field Trial. Our 1st generation trial involved the evaluation of two, first grade, universal, preventive interventions in collaboration with the Baltimore City Public Schools (BCPSS). Our use of the term “universal preventive intervention” reflects the fact that we intervened with an entire population of first grade school children¹⁵. This 1st generation trial was fielded in 19 Baltimore City schools with two consecutive cohorts of first graders in the 1985-86 and 1986-87 school years. Two theory-based preventive interventions were evaluated, which were exclusively based in the classroom and did not directly involve families. One intervention, the Good Behavior Game¹⁷ (GBG), was aimed at aggressive/disruptive and off-task behavior, whereas the other intervention, Mastery Learning^{18,19} (ML), targeted poor school achievement.

The results of this 1st generation JHU PIRC field trial yielded evidence that the proximal targets of aggressive/disruptive behavior and poor achievement were malleable^{20,21}, and that change in the proximal targets was associated with change in the distal outcomes in middle school²² and in early adulthood^{10,11,12}. In terms of the immediate impacts, the GBG resulted in significant—albeit modest—reductions relative to controls in aggressive/disruptive and off task behavior based on independent observations²¹ by the end of first grade, whereas Mastery Learning resulted in significant but modest improvement in standardized reading achievement²⁰. Dolan et al.²⁰ also reported significant beneficial impact of the GBG in terms of teacher ratings and peer nominations of aggressive/disruptive behavior in 1st grade. The GBG appeared to have its greatest proximal impact among boys manifesting mild to moderate elevations in aggressive/disruptive behavior at pre-test in the fall of first grade²⁰. With respect to longer term impact, Kellam and colleagues reported significant and beneficial impact of the GBG on antisocial behavior, violent crime, substance abuse/dependence, and high-risk sexual behavior at ages 19-20^{10,11,12}. Consistent with the variation seen in the immediate impact of the GBG in Dolan et al.²⁰, the greatest effects were found for males with mild to moderate elevations in pre-test levels of aggressive/disruptive behavior in 1st grade.

The 2nd Generation JHU PIRC Field Trial. Although promising, we were not satisfied with the magnitude of the effects of the 1st generation interventions on students' behavior and learning. Subsequently, we fielded our 2nd generation of JHU PIRC preventive interventions⁹. We first created an intervention condition wherein we combined the GBG with an academic intervention. The decision to combine the GBG with an academic intervention reflected the fact that in our 1st generation field trial the GBG had modest proximal impact on achievement, whereas Mastery Learning had an impact on early achievement, but had only a modest to moderate crossover, or indirect, effect on aggressive/disruptive behavior. Each intervention thus appeared to be specific to its own proximal target. Consequently, if we were to reduce early aggressive/disruptive behavior and improve academic achievement, both academic achievement and aggressive/disruptive and off-task behavior needed to be targeted in a single intervention condition.

In addition to combining the GBG with an academic intervention in our 2nd generation intervention trials, we also developed and fielded a universal, family-school partnership (FSP) intervention to contrast with the combination of the GBG and an academic intervention. Like the combination of the GBG with an academic intervention, the proximal targets of the FSP intervention were poor achievement and aggressive/disruptive and off-task behavior. The FSP intervention included a series of 9 workshops led by teachers and school mental health professionals, respectively, over the school year that focused on improving parent child

behavior management practices and support for their child's academic performance. The decision to add a family-based component was consistent with existing theory and the considerable empirical evidence of the important influences that families exert on their children's academic success^{23,24} and social development²⁵, along with the benefits of strong parent-teacher partnerships and parent involvement²⁶ on children's behavior and achievement.

The design of the 2nd generation JHU PIRC trial featured 3 first grade classrooms within each of 9 Baltimore City elementary schools. The three 1st grade classrooms in each of the nine elementary schools were randomly assigned to one of the two intervention conditions or to a control condition. In addition, children within each of the schools were randomly assigned to classrooms. We found significant proximal (elementary school)^{9,16}, intermediate (middle school)^{3,16}, and longer term (high school/early adulthood) intervention impacts on aggressive-disruptive behavior/conduct problems¹⁶ and academic outcomes^{3,9,27}. Both Jalongo et al.³ and Petras et al.¹⁶ provided evidence suggesting that the intermediate³ and longer term¹⁶ intervention impact on aggressive/disruptive behavior/conduct problems was in part a function of the proximal impact of the interventions on aggressive-disruptive behavior in early elementary school and on the parent-child relationship in terms of lower levels of parent rejection in late childhood/early adolescence³.

To summarize, both the immediate⁹ and longer-term results of the 2nd generation JHU PIRC trial^{16,27} supported our hypothesis that the combination of the GBG with an academic intervention would yield greater impact in terms of effect size on academic achievement than that seen in the 1st generation trials, wherein the GBG and Mastery Learning were examined separately²⁰. However, we did not see greater impact on aggressive-disruptive behavior as a result of our combining the GBG with an academic intervention. The family-school partnership did yield significant immediate benefits in terms of aggressive/disruptive behavior and academic achievement, but the breadth of the effects and their size were smaller than for the combination of the GBG and the academic intervention^{3,9}.

The 3rd Generation JHU PIRC Field Trial: The Combination of the GBG & PATHS. Given the combination of the GBG with an academic intervention did not yield greater improvement in aggressive/disruptive behavior than that seen in the 1st generation trial of the GBG alone, a seemingly logical next step would have been to combine the GBG + academic intervention condition with the FSP intervention, given the latter did have an impact on aggressive/disruptive behavior—albeit modest. But the costs and logistics involved in mounting a universal family-school partnership intervention proved daunting.

Consequently, we submitted a successful grant application to the Institute of Education Sciences (IES) in 2007, wherein we proposed to combine the GBG with a second and complimentary, evidenced-based, universal preventive intervention: PATHS. There are a number of reasons why we expected additive, if not synergistic effects, as a result of combining the two interventions. First, the efficacy of PATHS in terms of reducing aggressive/disruptive behavior and increasing prosocial behavior, social competence, inhibitory control and verbal fluency in the elementary school years had been demonstrated in a series of randomized controlled studies (CPPRG)^{28,29,30,31}. Second, PATHS seeks to accomplish reductions in aggressive/disruptive behavior via teacher led instruction aimed at facilitating emotion regulation, self-control, social problem-solving, and conflict resolution skills^{32,33}, whereas the GBG is based on social learning principles and provides teachers with an efficient means of managing student aggressive/disruptive and off-task behavior via reinforcement of the inhibition of these behaviors within a game-like context. The GBG, by increasing attention to task and reducing disruptive behavior in the classroom, may facilitate the acquisition of the emotion regulation, self-control, social problem-solving, and conflict resolution skills taught in PATHS. Third, the social learning based GBG may increase the likelihood that students' newly acquired skills would be appropriately prompted and reinforced by teachers. Consequently, the PATHS skills would be better learned and more frequently employed. Fourth, the increased teacher and child success, as a result of combining PATHS and the GBG, should minimize teacher and child discouragement and subsequent failure to participate or comply fully with the intervention regimens.

Our IES funded trial of the GBG+PATHS--or as we refer to it from hereon as PATHS to PAX--featured a group-randomized design, wherein 27-schools (grades K-5) were assigned to one or 3 conditions: 1) Comparison/Control; 2) GBG Alone; or 3) PATHS to PAX (GBG+PATHS). Approximately, 300 teachers and 5,000+ students participated in the trial and provided data, which included classroom observations and teacher ratings of student behavior at pre- and post-test over a 1-year period. The evidence from this group randomized trial, which was completed in 2012, suggested that PATHS to PAX resulted only in modest improvement over the GBG Alone in terms of aggressive/disruptive behavior and teacher outcomes (e.g., perceived behavior management self-efficacy)³⁴.

The Need for Research on the Combination of Evidence-based Universal, Indicated and Treatment Interventions. The relatively modest improvements found for PATHS to PAX (GBG+PATHS) over the GBG Alone served in part as the impetus for our testing the nesting of indicated and treatment interventions within our universal intervention: PATHS to PAX. Also moving us to evaluate such an integration was that despite evidence of long-term benefits of the GBG in terms of the reduction of antisocial behavior and drug use^{10,12} in our 1st and 2nd generation JHU PIRC trials, closer analyses of these data suggest that about half of those children in the highest trajectory of aggressive/disruptive behavior from grades 1-7 demonstrated no GBG impact in the short or long term¹¹. In addition, based on individual interview, focus group, and questionnaire data from our PATHS to PAX trial, the primary reason teachers gave for not implementing PATHS to PAX was because it did not prove helpful with their most aggressive/disruptive students. This was consistent with Han & Weiss' model³⁵ of the factors influencing teacher implementation of evidence-based interventions in school settings. More specifically, Han & Weiss³⁵ argue that teacher perception of the effectiveness of an intervention is a central factor in their level of its implementation. Relatedly, data from our PATHS to PAX trial suggested that the greater the number of highly aggressive/disruptive children in a PATHS to PAX classroom at baseline, the lower the level of teacher implementation of the GBG and PATHS.

Our rationale for expecting an added benefit from the combination of PATHS to PAX with an indicated and treatment intervention was that the latter interventions were more likely to be effective with the non-responders to PATHS to PAX. These non-responders typically represent the most aggressive/disruptive students in the classroom. We also hypothesized that the improvement in the behavior of the non-responders via the indicated or treatment intervention would increase teacher perception of the effectiveness of PATHS to PAX, which would lead to increased PATHS to PAX implementation. This increased implementation should then result in improved student outcomes overall, not just for the non-responders.

Our choice for an indicated and treatment intervention was the Incredible Years^{36,37,38,39,40}. The Incredible Years (IY) has been evaluated in multiple randomized controlled trials as a preventive⁴¹ and treatment^{37,38,39,42,43} intervention. IY has been found to be efficacious in reducing aggressive/disruptive behavior in the home and school over the short^{37,38,39,41,42,43} and long term^{38,44,45}. In addition, Webster-Stratton and colleagues report effects for the IY child component alone^{37,42,46}—the importance of which is highlighted by the relatively modest to moderate parent participation rates often found among urban and economically distressed populations⁹.

We also believed that there was a strong conceptual rationale for combining these three interventions. First, all three interventions share a common focus on facilitating the development of the child's capacity to self-regulate. Second, all 3 attempt to achieve that goal through the use of social cognitive learning theory principles to varying degrees. Third, the content of small group Dina and PATHS emanates from a common theory of socioemotional development^{6,7}.

Study Design

Overview of the Research Setting, Design, and Procedures for the Trial. The trial was conducted in the Baltimore City Public Schools (BCPS) which serves a predominantly African American population--84% of which are eligible for free or reduced lunch. We carried out a school-based, group-randomized trial (GRT) to determine whether the PATHS to PAX + Incredible Years arm yielded superior student and teacher outcomes, relative to the PATHS to PAX Alone arm. We also tested whether the PATHS to PAX + Incredible Years and the PATHS to PAX Alone arms both yielded superior student and teacher outcomes relative to the control arm. These comparisons with the control arm were only carried out to insure that in the case of no significant differences between the two active intervention arms the reason was not because both interventions failed to yield superior outcomes relative to the control arm. A GRT was required given randomization occurred at the level of the school. Four consecutive cohorts of 12 elementary schools for a total of 48 schools were randomly assigned to 1 of 3 conditions: 1) Control; 2) GBG+PATHS Alone; or 3) GBG+PATHS+IY. We confined the study to K-2 teachers given evidence from our most recent trial that the GBG is most effective in K-2.

We also recruited approximately ~ 25 K-2 students per school assigned to the GBG+PATHS+IY condition for participation in the ***IY child and parent groups*** across the four cohorts. Students were selected for inclusion in the IY intervention based on teacher completion of a checklist version of the Oppositional Defiant and Conduct Disorder modules of the teacher version of the Computerized-Diagnostic Interview Schedule for Children IV (C-

DISC IV). Those students who were sub-syndromal (falling just below the threshold number of symptoms/behaviors to meet DSM-IV diagnostic criteria for Oppositional Defiant or Conduct Disorder) and those who met diagnostic criteria for one or both of these disorders were recruited for inclusion in the IY groups. Randomization. The 12 schools making up each cohort were rank ordered based on school characteristics obtained from prior year archival records, including % Black, % free or reduced lunch, % males, % disciplinary removals, % receiving special education, number of students, and mean levels of standardized achievement scores. Schools adjacent in rank were grouped into triads, or sets of 3. Schools were then randomized to the 3 conditions from within these matched sets of 3. Timing of the Assessments. Classroom observations of student behavior, peer nominations, and child perceptions of peer acceptance were gathered in the fall (October) and spring (May) of the first year for each cohort, whereas teacher ratings of student behavior were gathered in the fall (October) and spring (May) of the first year for each cohort and at 1-year follow-up in Year 2 for each cohort.

Statistical Analysis Plan

Aims 1 & 2. Outcome Analyses. Trials Aims 1 and 2 were centered on testing whether the PATHS to PAX + Incredible Years arm yielded superior student and teacher outcomes relative to the PATHS to PAX Alone arm. We also tested whether the PATHS to PAX + Incredible Years and the PATHS to PAX Alone arms both yielded superior student and teacher outcomes relative to the control arm. These comparisons with the control arm were only carried out to insure that in the case of no significant differences between the two active intervention arms the reason was not because both interventions failed to yield superior outcomes relative to the control arm. The General Linear Mixed Model was employed given teachers were nested within schools and students nested within teachers and repeated observations nested in both. The General Linear Mixed Model is appropriate when there are multiple sources of random variation and all sources are distributed Gaussian. Murray and colleagues report that even in the case of violations of the Gaussian distribution assumption, the General Linear Mixed Model provides the same Type 1 error protection as the Generalized Linear Mixed Model^{47,48}. Importantly, Aims 1 & 2 outcomes included pre-test-post-test only (e.g., classroom observations, peer nominations, and teacher reported self-efficacy and burn out), pre-test, post-test and 12-month follow-up (e.g., teacher reports of student behavior). General Linear Mixed model analysis of covariance was used in the case of the pre-test-post-test, and pre-test and 1-year follow-up outcomes. In addition to intervention status, the baseline level of the outcome variable was included as a covariate. School was treated as a random effect. Given all the comparisons between conditions were planned and directional, no correction was made for the experiment-wise level of error since such a correction would have only been appropriate in the case of exploratory analyses. Results reported in the Outcome Measures section include the adjusted post-test means and standard errors for the planned comparisons between the 2 intervention arms and between the intervention and control arms.

References

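### Does a null result for adding Incredible Years become unreadable because the plan offers only control comparisons and names no interval?

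*Combined protocol and SAP*

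**What the plan says.** The Statistical Analysis Plan (Aims 1 & 2. Outcome Analyses) describes the aims this way: "centered on testing whether the PATHS to PAX + Incredible Years arm yielded superior student and teacher outcomes relative to the PATHS to PAX Alone arm". Each active arm is also compared with control, for one stated purpose, quoted here in part: "in the case of no significant differences between the two active intervention arms the reason was not because both interventions failed". In other words, a null should not be explained by neither programme beating control. The Study Design overview gives the same purpose.

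The Study Design overview lists the active arms as "2) GBG+PATHS Alone; or 3) GBG+PATHS+IY", so IY is the only designed difference between them. On who receives it: "We also recruited approximately ~ 25 K-2 students per school assigned to the GBG+PATHS+IY condition for participation in the". The sentence goes on to name the IY groups, which have child and parent components.

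On output, the SAP says: "Results reported in the Outcome Measures section include the adjusted post-test means and standard errors for the planned comparisons between the 2 intervention arms". The same is promised for each active arm against control. The SAP names no confidence interval, significance level, target difference or smallest worthwhile IY gain. The comparisons are called planned and directional, without saying whether tests are one- or two-sided.

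**The concern.** IY versus Alone is the trial's main question, and the only stated help with a null answer is a pair of comparisons that do not isolate IY. The Alone-versus-control comparison contains no IY at all. The IY-versus-control comparison tests the whole package and can succeed through the shared GBG+PATHS. A null main comparison with both arms beating control could mean that IY adds nothing, or that it adds something 16 schools per arm could not resolve. A reader deciding whether IY is worth its cost needs to know which gains remain possible, and that calls for an interval.

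A null is also plausible. Only about 25 children per school enter the IY groups, so a direct benefit is diluted in any outcome averaged over all K-2 students. The Rationale expects spillover ("This increased implementation should then result in improved student outcomes overall, not just for the non-responders") but does not size it.

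**Working it through.** **Plan's own figure.** 4 cohorts × 12 schools = 48 schools; 48 / 3 = 16 per arm. This agrees with the text. There is no power calculation to reproduce.

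**Inputs.** Only the 16 schools per arm and the 25 IY children per school describe this trial. The Rationale says of the previous trial, which covered 27 K-5 schools: "300 teachers and 5,000+ students participated in the trial". Halving for K-2 gives 5,000 / 27 / 2 = 92.6, about 93 students, and 300 / 27 / 2 = 5.6 teachers per school. Assumed: SD 1, ICC 0.02, 0.05 or 0.10, R² 0.5 or 0, and an Alone effect of 0.30 or 0.20 SD. Significance is two-sided 5% unless stated, with 48 − 3 = 45 degrees of freedom.

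**Step 1: width of the interval.** SE(IY − Alone) = √(2 × [ICC + (1 − ICC)/m] × (1 − R²) / 16); half-width = 2.014 × SE.

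| Outcome | R² | ICC 0.02 | ICC 0.05 | ICC 0.10 |
|---|---|---|---|---|
| Student, m = 93: SE | 0.5 | 0.044 | 0.061 | 0.083 |
| Student: half-width | 0.5 | 0.09 | 0.12 | 0.17 |
| Student: half-width | 0 | 0.12 | 0.17 | 0.24 |
| Teacher, m = 5.5: half-width | 0.5 | 0.22 | 0.24 | 0.26 |

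With m from 60 to 150, ICC up to 0.15 and R² from 0 to 0.5, the student half-width runs from 0.08 to 0.29 SD.

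**Step 2: can the interval be had from the promised output?** If the reported standard error is that of the difference, the interval is difference ± 2.014 × SE. If standard errors are per arm, SE(difference) is approximately √(SE₁² + SE₂²). At ICC 0.05 and R² 0.5 each arm's SE is 0.061/√2 = 0.043, and √(2 × 0.043²) = 0.061 again. The unstated degrees of freedom hardly matter: at m = 100, ICC 0.05 and R² 0.5, the half-width is 0.123 on 45 df and 0.125 on 30.

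**Step 3: what does the control check tell the reader after a null?** A simulation drew 1,000,000 sets of three arm means per scenario, with a chi-square(45) variance estimate. At R² 0.5 and m = 93, among two-sided nulls:

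| Both arms beat control | ICC 0.02 | ICC 0.05 | ICC 0.10 |
|---|---|---|---|
| Alone +0.30, IY adds 0 | 100% | 99.6% | 91% |
| Alone +0.30, IY adds 0.15 | 100% | 100% | 98% |
| Alone +0.20, IY adds 0 | 99% | 83% | 52% |
| Alone +0.20, IY adds 0.15 | 100% | 97% | 77% |

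Passing is never less likely when IY works, so it cannot support the reading that IY adds nothing. Nor is it always flat: at Alone +0.20 SD it moves from 52% to 77%.

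**Step 4: what would the interval tell the reader?** The table gives the probability that the 95% interval excludes a gain of 0.15 SD, among two-sided nulls, for student outcomes.

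| | ICC 0.02 | ICC 0.05 | ICC 0.10 |
|---|---|---|---|
| IY adds 0, R² 0.5 | 94% | 68% | 42% |
| IY adds 0.15, R² 0.5 | 29% | 8% | 4% |
| IY adds 0, R² 0 | 67% | 39% | 23% |

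For teacher outcomes at R² 0.5, with IY adding 0, the figure is about 19 to 25%.

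**Step 5: dilution.** 25 / 93 = 27%. A gain of 0.3 SD confined to IY children averages 0.3 × 0.27 = 0.08 SD over all K-2 students, and 0.8 SD averages 0.22 SD, before any spillover. The documents do not say which students are analysed.

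**The case for a change.** The best case for a change is that this is the main contrast, and the interval carries information that the check does not. If IY really adds 0.15 SD and Alone is at +0.30 SD (R² 0.5), a null with both arms beating control occurs in 8, 33 and 56% of trials at ICC 0.02, 0.05 and 0.10 (4, 22 and 44% with one-sided tests). Even after the check has passed, at ICC 0.10, the interval excludes 0.15 SD in 42% of nulls if IY adds nothing, against 4% if it adds 0.15. The SAP does not say whether the promised standard errors are per arm or of the difference, gives no level, and leaves sidedness open ("Given all the comparisons between conditions were planned and directional"). Nothing commits the authors to an interval, and adding one costs a line of reporting.

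The logic stands: beating control says nothing about the IY increment on its own. Two parts are weaker. The check is not uninformative in general, as the Alone +0.20 SD rows show. The interval's value also depends on a favourable R²: without covariate gain it excludes 0.15 SD in only 23 to 67% of nulls when IY adds nothing, and for teacher outcomes in about a fifth to a quarter even at R² 0.5. The simulation also ignores the teacher-level clustering that the SAP describes, and the dilution figures set aside the spillover that the Rationale expects.

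**Conclusion.** No change to the plan is needed. The control comparisons are given one job, ruling out failure of both programmes, and they do it. The plan draws no conclusion of no benefit from a null. The main contrast is already to be reported with adjusted means and standard errors, and an analyst gets the interval from these by one multiplication, or closely enough if the standard errors are per arm. The SAP points to an Outcome Measures section that is not in these documents, so whether an interval appears there cannot be told. What is missing is a sentence of reporting detail; supplying it would alter no estimate, test or design feature.

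Readers should keep the narrow point in mind: after a null, both arms beating control is not evidence that IY adds nothing. The adjusted IY-minus-Alone difference with its interval is the natural thing to report. Because the plan is written in the past tense, any smallest worthwhile gain chosen now would be post hoc. All SD-scale figures rest on assumed ICC, R² and school sizes borrowed from the previous trial, and they do not show that this trial is underpowered.

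### As described, the 1-year teacher-rating ANCOVA leaves out May scores and states no handling of missing Year-2 ratings, so arm-related loss could bias the contrast between the arms with and without Incredible Years

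*Combined protocol and SAP*

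**What the plan says.** The Timing of the Assessments text (Study Design) has teacher ratings of student behaviour collected in October and May of the first year and again "at 1-year follow-up in Year 2 for each cohort". Aims 1 & 2, Outcome Analyses (SAP) accordingly lists an outcome type with "pre-test, post-test and 12-month follow-up (e.g., teacher reports of student behavior" as its example.

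The same SAP paragraph justifies the mixed model by the nesting of teachers in schools, with "students nested within teachers and repeated observations nested in both". It then says what was fitted: "General Linear Mixed model analysis of covariance was used in the case of the pre-test-post-test, and pre-test and 1-year follow-up outcomes". Besides intervention status, "the baseline level of the outcome variable was included as a covariate. School was treated as a random effect". The comparisons are described this way: "Given all the comparisons between conditions were planned and directional". No alpha is given.

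The paragraph names no May term in the 1-year analysis, no time effect, no arm-by-time contrast and no within-student covariance. It gives no missing-data method or assumption, no sensitivity analysis and no attrition figure.

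**The concern.** The fitted-model sentence names two pairs: October with May, and October with Year 2. Taken plainly, the 1-year model has the Year-2 score as outcome and the October score as covariate. A student with October and May ratings but no Year-2 rating enters the first analysis and not the second, although the May score says something about the missing value.

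With a constant treatment effect, that ANCOVA copes with loss that depends on arm and October score. It does not cope with loss that also depends on May behaviour when the strength of that dependence, or the loss rate, differs by arm. If the worse-behaved are lost more from the arm with Incredible Years (IY), the contrast favours IY. If they are lost more from the PATHS to PAX Alone arm, it goes against IY.

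A difference by arm is conceivable, because only the IY arm offers child and parent groups to its most symptomatic students (about 25 per school). The contrast at stake is the trial's main comparison, at its longest follow-up.

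**Working it through.** The plan has no power, attrition or missing-data figure to reproduce. The only design arithmetic is the number of schools: "Four consecutive cohorts of 12 elementary schools for a total of 48 schools were randomly assigned to 1 of 3 conditions", so 4 × 12 = 48 and 48/3 = 16 per arm.

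**Assumed inputs (not in the documents unless noted)**
- Correlations: October–May 0.6, May–Year 2 0.5, October–Year 2 0.45.
- May effect 0.2 SD, no 1-year effect, ICC 0.05.
- 93 students per school. The Rationale reports 5,000+ students in 27 K-5 schools in the previous trial, and here "We confined the study to K-2 teachers". So 5,000/27 × 3/6 = 92.6.
- Loss is logistic in May score. Odds ratios (OR) are per SD, and higher scores mean worse behaviour.

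**Standard error of a two-arm contrast**

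SE = √[(2 × 0.05 + 0.95/m₁ + 0.95/m₂)/16], with m = 93 × (1 − loss). At 25% loss in both arms, m = 69.75 and SE = √[(0.10 + 0.0272)/16] = 0.089. Multiplying by √(1 − 0.45²) = 0.893 for baseline adjustment gives 0.080. Over 15–35% loss the range is 0.079–0.091.

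**Bias of the completer ANCOVA**

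Bias is the completer estimate minus the no-loss estimate, from 2,000,000 simulated students per arm. It is shown in absolute value. Two-sided error is P(|Z + bias/SE| > 1.96).

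| Loss mechanism | Loss | Bias (SD) | Two-sided type I error |
|---|---|---|---|
| OR 2 v 1.5 | 15 / 25 / 35% in both arms | 0.009 / 0.014–0.015 / 0.019–0.020 | at most 5.7% |
| OR 2 in both arms | 15 v 25% | 0.014–0.015 | 5.3–5.4% |
| OR 2 in both arms | 15 v 35% | 0.029 | 6.2–6.6% |
| OR 2 v 1.5, differences add | 25 v 15% | 0.023–0.024 | – |
| OR 2 v 1.5, differences offset | 15 v 25% | 0.000 | – |
| OR 2 in one arm, 1 in the other | 15 / 25 / 35% | 0.022–0.023 / 0.037 / 0.051–0.052 | 5.7–6.0 / 6.9–7.6 / 8.7–9.8% |
| OR 2 in both arms | equal | under 0.001 | – |

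Example: 0.051/0.0906 = 0.56 SE, which gives 8.7%. In every row, a joint model that uses May comes within 0.001 SD of the no-loss estimate.

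A clustered check (4,000 trials per case, 16 schools per arm, t test on 30 df) gave rejection rates of 0.051–0.056 for OR 2 v 1.5 at 35% loss, 0.059–0.064 for OR 2 in both arms at 15 v 35%, and 0.086–0.087 for one arm only at 35%.

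The plan calls its comparisons directional. With an assumed one-sided 5% test, false IY superiority in those three cases is 7.5–7.9%, 9.2–9.9% and 13.9–15.5% if the larger loss or selection is in the IY arm. It is 2.9–3.1%, 2.2–2.4% and 1.1–1.3% if it is in the Alone arm.

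**Sensitivity to the assumptions**
- Other correlations (October–May 0.5–0.7, May–Year 2 0.4–0.6, October–Year 2 0.40–0.50): 0.005–0.030 SD for OR 2 v 1.5 at 15–35% loss; 0.010–0.041 for OR 2 in both arms at 15 v 25–35%; 0.024–0.075 for one arm only at 25–35%.
- One arm only at 30% loss, over a partly different set of correlations and a 0.2 SD effect: 0.027–0.072 SD at OR 1.65 and 0.050–0.129 at OR 2.7.

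**Effect not constant across baseline**

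Suppose the IY effect is confined to the top 25/93 = 27% at baseline, at 0.6 SD in May and 0.4 SD in Year 2. The average Year-2 effect is 0.27 × 0.4 = 0.11 SD. Loss that depends on baseline only (OR 2), equal in both arms at 25–35%, shifts the ANCOVA by 0.024–0.031 SD and the joint model by 0.010–0.013. Equal May-dependent loss shifts the ANCOVA by 0.008–0.012. The null is not affected.

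**Loss that depends on the unseen Year-2 score**

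At 25% loss the bias is 0.051 SD for completers and 0.046 for the joint model with OR 2 v 1.5, and 0.129 and 0.116 with OR 2 in one arm only. The share removed is 0.005/0.051 = 10% and 0.013/0.129 = 10%. With three other sets of correlations (30% loss, OR 1.65 in one arm), the bias falls from 0.124 to 0.117, 0.108 to 0.088 and 0.121 to 0.074, so 6%, 19% and 39% is removed.

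**The case against.** The strongest reply is that the model is inferred. The SAP cites repeated observations as a reason for a mixed model and lists teacher reports as a three-wave outcome. The ANCOVA sentence lists outcome types and does not say that two separate models were fitted. This stands in part: a joint model is not excluded, and a reader who concludes that the trial certainly discarded May data goes beyond the text. But the repeated-observations phrase explains the choice of model class. The sentence on what was fitted names baseline-adjusted pairs and none of the terms that a joint model needs. The missing-data silence remains on either reading.

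The second reply is that the bias rarely matters. Every input except 16 schools per arm is assumed or borrowed from the previous trial. Modest differences move two-sided error by under one percentage point. The SAP's closing sentence speaks of adjusted post-test means and does not single out the 1-year contrast. This limits the severity. It does not support a general statement that the bias is small outside extreme cases, because that too rests wholly on assumed inputs. OR 2 in both arms with 15 v 35% loss is not an extreme selection pattern, yet it roughly doubles an assumed one-sided 5% error when the larger loss is in the IY arm.

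The third reply is that the remedy is partial: it leaves some shift when the effect varies with baseline, and does little when loss depends on the unseen score. Both points are right, and the fix allows for them.

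**Conclusion.** The point holds as a gap in the stated analysis with a cheap improvement available. Its severity is minor to moderate. On the plain reading, May ratings do not inform the 1-year contrast, and no handling of missing Year-2 ratings is given.

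Under the stated assumptions the bias is about 0.00–0.03 SD when arms differ modestly in loss or selection (up to 0.041 under other correlations). It is about 0.03–0.05 SD at 25–35% loss when loss depends on May score in one arm only, up to about 0.07 under other correlations, and more with stronger selection. The assumed SE is 0.08–0.09 SD. Equal loss and selection give near-zero bias only if the effect is constant across baseline. If the effect is concentrated in the most symptomatic students, equal loss can still shift the estimate by about 0.01–0.03 SD.

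A reader might infer that the 1-year result is biased, or that it favours IY. The documents support neither: they report no attrition, and the direction depends on which arm loses more of its worse-behaved students. This mechanism does not touch the May contrasts, observations, peer nominations or teacher outcomes. The plan states no missing-data rule for those either, so this does not clear them of other problems.

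**What to change.** - State whether May and Year-2 teacher ratings were modelled jointly, and how missing ratings were handled.
- For teacher ratings, fit May and Year-2 scores as repeated outcomes in one mixed model. Use arm × time and baseline × time terms, unstructured within-student covariance, and the planned school random effect (one per time). Include every student with a baseline and at least one post-baseline rating.
- Report the contrast between the two active arms at each time, and rating counts by arm and wave.
- Because the effect may vary with baseline, check the result with arm × baseline × time terms, averaged over the full baseline distribution.
- State that the model removes this bias only when loss depends on observed scores, and that it removed only about 10% in the main runs where loss depended on the unseen Year-2 score. Add a delta-shift sensitivity analysis by arm for that case.

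Triad and teacher or classroom effects are a separate question. The documents do not say who rated students in Year 2.

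The cost is some SAP wording, one refit with its check, a table of counts and one sensitivity analysis. No new data are needed. The downside is a slightly more complex model.
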